9.1.1. Incidence of Adverse Events

An overall summary table of AEs will present the number of patients with at least one event, the total number of events, and 95% CI (zetomipzomib – placebo) for the following:

- Any TEAE
- Any IMP-Related TEAE
- Any Grade 3 or 4 TEAEs
- Any Serious TEAE
- Any IMP-Related Serious TEAE
- AESI by the categories: Systemic Injection Reaction (SIR) and thrombotic microangiopathy (TMA) which also includes thrombotic thrombocytopenic Purpura (TTP) and hemolytic uremic syndrome (HUS)
- Any TEAE leading to Discontinuation from Study
- Any TEAE leading to study treatment Discontinuation

- Any TEAE leading to Dose Reduction
- Any TEAE leading to Dose Interruption
- Any TEAE Leading to Death

The number and percentage of patients with at least one TEAE will be summarized by treatment group (30 mg zetomipzomib, 30 mg Placebo, 60 mg zetomipzomib, 60 mg Placebo, 30mg and 60mg zetomipzomib, 30mg and 60mg Placebo) and overall (all patients).

All TEAEs will also be summarized by PT for each treatment group. PTs will be sorted in descending order of frequency in the combined zetomipzomib 30 mg and 60 mg group. A separate summary of the most common TEAEs (≥5% of patients in any treatment arm) will be presented in a similar manner.

All AEs will be summarized by PT only (without SOC) in descending order sorted by combined zetomipzomib 30 mg and 60 mg group

All AEs will be presented in a listing, with TEAEs clearly identified.

9.1.2. Relationship of Adverse Events to Study Drug

Adverse events will be classified as related to zetomipzomib or placebo or not related to zetomipzomib or placebo. Missing relationship status will be imputed as related.

The number and percentage of patients with at least one related TEAE will be summarized by treatment group and overall. Related TEAEs will be further summarized by SOC and PT.

9.1.3. Adverse Events by Maximum Severity

Severity of AEs will be graded according to the National Cancer Institute-Common Terminology Criteria for Adverse Events (NCI-CTCAE) Version 5.0 or higher. Grades are as follows:

- Grade 1 = Mild
- Grade 2 = Moderate
- Grade 3 = Severe
- Grade 4 = Life-threatening
- Grade 5 = Fatal

The number and percentage of patients with TEAEs will be summarized by SOC, PT, and maximum severity for each treatment group Patients with multiple occurrences of the same event will be counted only once in the numerator, at the maximum severity. Missing severity will be imputed as severe (Grade 3).

9.1.4. Serious Adverse Events

The number and percentage of patients with at least one SAE will be summarized by treatment group and overall. SAEs will be further summarized by SOC and PT and by PT only in descending order. Missing serious status will not be imputed.

SAEs related to study treatment will be summarized separately by PT as follows:

- SAEs leading to death
- SAEs leading to study treatment withdrawal
- SAEs leading to Dose Reduction*
- SAEs leading to Dose Interruption

All SAEs will be presented in a separate listing.

9.1.5. Adverse Events of Special Interest

The following adverse events of special interest (AESIs) have been identified in this study:

- Systemic injection reactions (SIRs)
- Thrombotic microangiopathy (TMA)

SIR events will be identified directly on the Adverse Events eCRF page. TMA events will be identified using the preferred terms "Thrombotic microangiopathy", "Thrombocytopenic purpura", or "Haemolytic uraemic syndrome".

AESIs will be summarized in a stand-alone table for the Primary Analysis and the final analysis by SOC and PT. The number and percentage of patients with at least one AESI will be summarized by treatment group and overall. AESIs will be further summarized by SIR or TMA, PT.

Summaries will be presented for:

- AESIs related to IMP
- AESIs leading to dose reduction
- AESIs leading to early study treatment discontinuation
- Grade 1, 2, 3 and 4 AESIs
- AESIs by maximum severity

All AESIs will be presented in a separate listing.

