### 9.5. Adverse Events of Special Interest

An adverse event of special interest (AESI) is one that is of scientific and medical concern specific to the Sponsor's product or program, for which ongoing monitoring and rapid communication by the Investigator to the Sponsor can be appropriate, regardless of the seriousness, expectedness, or relatedness of the AE to the administration of zetomipzomib or placebo.

SIRs and thrombotic microangiopathy have been identified as AESIs. Any Grade 3 or higher AESIs should be reported within 24 hours using the AE eCRF.

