## 9.5.2. Thrombotic Microangiopathy

Cases of thrombotic microangiopathy, including thrombocytopenic purpura and hemolytic uremic syndrome, have been described with the proteasome inhibitors, bortezomib, carfilzomib, and ixazomib. The clinical presentation of thrombotic microangiopathy typically includes fever, microangiopathic hemolytic anemia (with schistocytes on blood smear), thrombocytopenia, renal failure, purpura, and neurological manifestations. Patients should be monitored for signs and

symptoms of thrombocytopenic purpura/hemolytic uremic syndrome. If the diagnosis is suspected, such as with any acute changes in renal function, thrombocytopenia or intravascular hemolytic anemia, interrupt zetomipzomib or placebo administration and evaluate (refer to Section 8.1.2). Missed doses should be addressed as per Section 6.1.3.2. If the diagnosis of thrombocytopenic purpura/hemolytic uremic syndrome is excluded, zetomipzomib or placebo may be resumed. If the diagnosis is confirmed, zetomipzomib or placebo must be permanently discontinued (refer to Section 8.1.2).

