TTP	thrombotic thrombocytopenic purpura
ULN	upper limit of normal
UPCR	urine protein to creatinine ratio
VAS	visual analog scale
WHO	World Health Organization
WOCBP	women of childbearing potential

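### The preferred-term list that identifies thrombotic microangiopathy in SAP 9.1.5 omits thrombotic thrombocytopenic purpura, which SAP 9.1.1 counts within this AESI

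*SAP*

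**What the plan says.** Protocol 9.5 sets the AESIs: "SIRs and thrombotic microangiopathy have been identified as AESIs". Protocol 9.5.2 explains the concern by reference to other proteasome inhibitors: "Cases of thrombotic microangiopathy, including thrombocytopenic purpura and hemolytic uremic syndrome, have been described". The protocol here uses the shorter name, without the word thrombotic before it.

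SAP 9.1.1 plans an overall AE table with AESI rows by category. It describes the second category as "thrombotic microangiopathy (TMA) which also includes thrombotic thrombocytopenic Purpura (TTP) and hemolytic uremic syndrome (HUS". The SAP abbreviation list expands TTP in the same way, as "thrombotic thrombocytopenic purpura".

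SAP 9.1.5 says how AESIs are found in the data. For systemic injection reactions, "SIR events will be identified directly on the Adverse Events eCRF page". For the other category, "TMA events will be identified using the preferred terms", followed by three terms: thrombotic microangiopathy, thrombocytopenic purpura and haemolytic uraemic syndrome. The section then plans a stand-alone AESI table, several summaries (related to study drug, leading to dose reduction, leading to early treatment discontinuation, by grade, by maximum severity) and a separate AESI listing.

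**The concern.** SAP 9.1.1 and SAP 9.1.5 describe the same category with different contents. The first says TTP is in it. The second, which a programmer would implement, has no TTP term and has a differently worded one in its place.

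Matching on preferred terms is literal. An event coded to a term that is not on the list is not selected, however close its meaning. SAP 9.1.5 gives TMA no second route: no eCRF flag (as for systemic injection reactions) and no standardised query with medical review (as SAP 9.1.6 provides for opportunistic infections). Every AESI output in SAP 9.1.5 depends on this one rule.

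For a rare event that the protocol singles out, the AESI table is where a reader looks first. A table showing no TMA while a TTP case sits elsewhere in the report would mislead that reader, and two tables in the same report might give different TMA counts.

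**Working it through.** The plan states no figure on this point, so the check is a comparison of the text, followed by simple arithmetic for scale.

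**Step 1. Components against terms.**

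| Component named in SAP 9.1.1 | Matching term in SAP 9.1.5 |
|---|---|
| Thrombotic microangiopathy | Thrombotic microangiopathy |
| TTP | None by name; the list has thrombocytopenic purpura |
| HUS | Haemolytic uraemic syndrome |

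Two of the three components are matched by name and one is not.

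**Step 2. Is the difference intended?** The changes to the planned analysis in SAP section 13 do not mention it. The SAP 9.1.5 sentence is complete, so nothing has been lost to redaction. The wording probably comes from Protocol 9.5.2, which uses the shorter name in prose; this is an inference. In the protocol the surrounding clinical description makes the thrombotic meaning clear. A term list carries no such context.

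**Step 3. What follows when the rule is run.** SAP 9.1 codes AEs in MedDRA 26.1 or higher. There are two cases.

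- If the dictionary holds TTP as a preferred term of its own, a TTP event is not selected by SAP 9.1.5. It is absent from the stand-alone AESI table, the AESI summaries and the AESI listing. The TMA row in SAP 9.1.1 then either includes it, if programmed from that section's own description, and disagrees with SAP 9.1.5; or omits it, if programmed from the SAP 9.1.5 list, and contradicts its own description.
- If the dictionary places TTP under one of the three listed terms, no event is lost and only the wording needs aligning.

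**Step 4. Where the event still appears.** SAP 9.1.1 puts it in the TEAE summaries by preferred term and in the listing of all AEs. If serious, it is in the SAE tables and listing (SAP 9.1.4). If it led to stopping treatment, it is in the discontinuation table and listing (SAP 9.1.7).

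**Step 5. Scale of one case.** The planned arm is 83 patients with Class III/IV +/-V disease plus up to 10 with pure Class V, so 83 to 93. The safety population takes in both groups.

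- Planned arm: 1/93 = 1.1% to 1/83 = 1.2%.
- After the maximum 50% increase in Class III/IV +/-V patients: 83 × 1.5 = 124.5, or 134.5 with pure Class V; 1/134.5 = 0.7% to 1/124.5 = 0.8%.
- SAP 9.1.1 also shows the 30 mg and 60 mg placebo groups separately, each about half of the pooled placebo group: 1/46.5 = 2.2% to 1/41.5 = 2.4%.

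**The case against.** A fair defence has four parts.

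First, the consequence depends on MedDRA, which neither document reproduces. That stands. The loss of a TTP event is conditional on how the dictionary holds the term, although the mismatch between the two SAP sections does not depend on it.

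Second, a reader might infer that a TTP case would vanish from the safety report. The documents do not support this. The routes in Step 4 do not use the AESI term list. In addition, Protocol 9.5 asks for rapid reporting of AESIs of Grade 3 or higher, and under SAP section 12 the IDMC reviews cumulative unblinded safety data. Neither is said to depend on the list. The gap is confined to the AESI outputs.

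Third, a reader might infer that one missed case would change a conclusion of the trial. Nothing in the documents supports that either. The AESI summaries are descriptive, and no stopping rule is tied to this table.

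Fourth, a reader might infer that thrombocytopenic purpura is a wrong entry that would inflate the TMA count, since Protocol 4.2 admits patients with lupus-related thrombocytopenia. But Protocol 9.5.2 itself places that term under TMA, and a broad search for a rare safety signal is a defensible choice. The AESI table is broken down by preferred term, so a reader can see which term produced each count. Medical review of that term before counting it is a preference and not a necessary correction.

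None of this explains why the list lacks a component that SAP 9.1.1 names.

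**Conclusion.** The point holds as an internal inconsistency in the SAP with a limited consequence. One of the three components that SAP 9.1.1 assigns to the TMA AESI has no matching term in SAP 9.1.5. Provided that TTP is a separate preferred term in the dictionary version used, a TTP event would be missing from the stand-alone AESI tables and listing, and the SAP would be open to two different TMA counts. For an AESI where few or no cases may occur, a single case can be the difference between none and some in that display. The effect does not extend to the general TEAE, SAE or discontinuation outputs, and no efficacy analysis or formal safety decision depends on it. It should be corrected because the correction is nearly free.

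**What to change.** Before the AESI outputs are programmed:

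1. Check how the MedDRA version in use holds TTP.
2. Add thrombotic thrombocytopenic purpura to the term list in SAP 9.1.5 so that it matches SAP 9.1.1, and have both sections use the same list.
3. State whether the broader thrombocytopenic purpura term, which follows the wording of Protocol 9.5.2, is meant to stay. If it stays, blinded medical review of events under it, on the lines of SAP 9.1.6, is optional.

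The cost is one added term, one clarifying sentence and a dictionary look-up. No new data are collected and no efficacy analysis is affected.

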9.1.6. Opportunistic Infections

Opportunistic infections of interest will be identified through blinded manual review by Kezar's Medical Monitor.

Opportunistic infections in the STANDARDISED MedDRA QUERIES (SMQs) will be summarized in a stand-alone table for the Primary Analysis and the Final Data Analysis. The table will include all TEAEs identified as opportunistic infections using the following methods:

^{*}Dose reduction due to AE is only permitted in the zetomipzomib or placebo 60 mg treatment group; no dose reduction is permitted in the 30 mg group.

Step 1: The study programming team will pull out all TEAEs based on the SMQs of Opportunistic infections and produce an Excel spreadsheet with all TEAEs recorded up until the data cut.

- **Step 2:** The study Medical Monitor and Safety Physician will review the TEAEs in the provided spreadsheet to determine whether each one of the pulled TEAEs will be considered an opportunistic infection. The criteria will be based on their medical judgement.
- **Step 3:** The study Medical Monitor and Safety Physician will provide a list back to programming indicating which events should be flagged as an opportunistic infection.
- **Step 4:** The data will be integrated into the ADAM data sets so that opportunistic infection tables and listings can be created.

The number and percentage of patients with at least one opportunistic infection will be summarized by treatment group and overall. Opportunistic infections will be summarized by SOC and PT in the following categories:

- Opportunistic infections related to IMP
- Opportunistic infections leading to dose reduction
- Opportunistic infections leading to dose interruptions
- Opportunistic infections leading to early treatment termination
- Grade 3 and 4 Opportunistic infections
- Opportunistic infections by maximum severity

All opportunistic infections will be presented in a separate listing.

9.1.7. Adverse Events Leading to Treatment Discontinuation

The number and percentage of patients with at least one TEAE leading to early discontinuation of study treatment will be summarized by treatment group and overall. TEAEs leading to early discontinuation of study treatment will be further summarized by SOC and PT.

TEAEs leading to discontinuation of study treatment will be presented in a separate listing.

9.1.8. Adverse Events Leading to Study Discontinuation

The number and percentage of patients with at least one TEAE leading to early study discontinuation will be summarized by treatment group and overall. TEAEs leading to early study discontinuation will be further summarized by SOC and PT.

TEAEs leading to study discontinuation will be presented in a separate listing.

9.1.9. Adverse Events Leading to Dose Reduction

Dose reduction due to AE is only permitted in the zetomipzomib or placebo 60 mg treatment group; no dose reduction is permitted in the 30 mg group.

The number and percentage of patients with at least one TEAE leading to dose reduction will be summarized by treatment group and overall. TEAEs leading to dose reduction will be further summarized by SOC and PT.

TEAEs leading to dose reduction will be presented in a separate listing.

9.1.10. Adverse Events Leading to Dose Interruption

The number and percentage of patients with at least one TEAE leading to dose interruption will be summarized by treatment group and overall. TEAEs leading to dose interruption will be further summarized by SOC and PT.

TEAEs leading to dose interruption will be presented in a separate listing.

9.1.11. Death

The number and percentage of patients with at least one TEAE leading to death will be summarized by treatment group and overall. TEAEs leading to death will be further summarized by SOC and PT.

TEAEs leading to death will be presented in a separate listing, to include cause of death and death certificate availability information.

Any outcome of death without a corresponding fatal TEAE will be presented in a separate listing, to include cause of death and death certificate availability information.

9.1.12. Exposure-Adjusted Incidence Rates

Exposure will be calculated within each treatment group as the total time at risk of the event across all patients. Exposure will be calculated differently depending on whether the subject did or did not experience the event in question. For patients who experienced the event, exposure is calculated as the number of days from the first dose of study treatment to the first occurrence of the event. For patients who did not experience the event, exposure is calculated as the number of days from first dose of study treatment to the end of study, inclusive. End of study is defined as the minimum of (treatment discontinuation date, treatment completion date, death date, lost to follow-up date).

The incidence rate (IR) for the given preferred term is calculated within treatment group as the number of patients (n) experiencing at least one occurrence of the event divided by the total time at risk for all patients in the treatment group. EAIR for the given preferred term will be computed as the number of events / 100 years of exposure. The difference (zetomipzomib – placebo) between EAIR along with a 95% CI for the difference will be reported separately for the zetomipzomib 30 mg and 60 mg dose groups using the normal approximation.

EAIR =
$$\frac{n}{T} = \frac{n}{\sum t_i}$$

The test statistic is given by (z=zetomipzomib, p=placebo):

$$E = \left(\frac{n_z}{T_z} - \frac{n_p}{T_p}\right) / \sqrt{\frac{n_z}{T_z^2} + \frac{n_p}{T_p^2}}$$

The 95% CI for the difference in EAIR will be calculated as follows:

$$\left(\frac{n_z}{T_z} - \frac{n_p}{T_P} \right) - Z_{\alpha/2} \sqrt{\frac{n_z}{T_z^2} + \frac{n_p}{T_p^2}} \ , \ \left(\frac{n_z}{T_z} - \frac{n_p}{T_P} \right) + Z_{\alpha/2} \sqrt{\frac{n_z}{T_z^2} + \frac{n_p}{T_p^2}}$$

Summary tables presenting the number and percentage of patients, exposure time, EAIR, and treatment comparisons will be provided for the following:

- TEAEs, overall and by SOC and PT
- TEAEs \geq Grade 3 by SOC and PT
- Serious TEAEs, overall and by SOC and PT
- TEAEs by severity grade with incidence of 5% and higher

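### The normal-approximation CI for exposure-adjusted AE rate differences (SAP 9.1.12) has zero width at 0 vs 0 and can under-cover rare terms whose true rates differ; the EAIR sentence should also count patients, not events

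*SAP*

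**What the plan says.** SAP Section 9.1.12 gives the EAIR difference (zetomipzomib minus placebo) with a 95% CI, which "will be reported separately for the zetomipzomib 30 mg and 60 mg dose groups using the normal approximation". The displayed interval is (n_z/T_z - n_p/T_p) ± Z·√(n_z/T_z² + n_p/T_p²). The statistic E is the same difference divided by the same square root.

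The tables cover all TEAEs and Grade 3 or higher TEAEs by SOC and PT, and "Serious TEAEs, overall and by SOC and PT". Only the table by severity grade has a frequency threshold (5%). The section has no rule for zero or small counts.

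On the numerator, the section first defines the incidence rate as the "number of patients (n) experiencing at least one occurrence of the event divided by the total time at risk". The next sentence reads "EAIR for the given preferred term will be computed as the number of events / 100 years of exposure". The displayed formula is n/T. For a patient with the event, "exposure is calculated as the number of days from the first dose of study treatment to the first occurrence of the event".

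**The concern.** A Wald interval for a difference of two Poisson rates takes its variance from the observed counts. An arm with no affected patients therefore adds no variance, and two such arms give an interval of no width. Each dose is compared with placebo separately, so this happens for any preferred term seen only in the other dose group. The table would then show a 95% interval of [0, 0], as if a difference had been ruled out, where the data cannot exclude several affected patients per 100 PY in either direction. For rare terms with a real difference, an interval labelled 95% may cover much less often.

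The second issue is wording. Events divided by time to first event is not a rate, because later events are counted while the time in which they occur is not.

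**Working it through.** **Inputs.** SAP Section 3.1 plans about 83 plus up to 10 patients per group and 52 weeks of dosing, so at most 93 × 1 = 93 PY per arm. The documents give no drop-out figure and no AE rates. I assume 80 PY per arm to allow for early stopping, show 93 PY as the upper end, and state the assumed rates. Section 9.1.12 does not name the placebo comparator; I take pooled placebo. The plan states no EAIR figure to reproduce.

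**Step 1: no affected patients in either arm.** With n_z = n_p = 0 the difference is 0 and the variance is 0/T_z² + 0/T_p² = 0. The CI is [0, 0] and E = 0/0. This needs no assumption.

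- Score interval: keep every difference D with |observed difference - D| / √(r_z/T_z + r_p/T_p) ≤ 1.96, where r_z and r_p are the maximum-likelihood rates restricted to differ by D. At 0 vs 0 and D > 0, r_z = D and r_p = 0, so the condition is √(D·T) ≤ 1.96, or D ≤ 3.84/80 = 4.8 per 100 PY. By symmetry the interval is -4.8 to +4.8.
- Exact Poisson limits combined by square-and-add: the upper limit for zero events is 3.69, and 3.69/80 = 4.6, so -4.6 to +4.6.
- At 93 PY the two intervals are ±4.1 and ±4.0.

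**Step 2: coverage.** For expected counts λ_z and λ_p, coverage is the sum over all pairs (x, y) of Poisson(x; λ_z) × Poisson(y; λ_p) for those pairs whose interval contains the true difference. The chance of a zero-width interval is exp(-λ_z - λ_p). At 80 PY per arm:

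| True rates per 100 PY, drug vs placebo | Expected counts | SAP interval | Score interval | Chance of [0, 0] |
|---|---|---|---|---|
| 1.25 vs 0 | 1.0 / 0 | 63% | 100% | 37% |
| 1.0 vs 0.5 | 0.8 / 0.4 | 69% | 100% | 30% |
| 1.5 vs 0.25 | 1.2 / 0.2 | 70% | 99% | 25% |
| 2 vs 0.5 | 1.6 / 0.4 | 80% | 99% | 14% |
| 3 vs 1 | 2.4 / 0.8 | 90% | 98% | 4% |
| 0.5 vs 0.5 | 0.4 / 0.4 | 99.9% | 99.9% | 45% |
| 1 vs 1 | 0.8 / 0.8 | 99% | 99% | 20% |
| 2 vs 2 | 1.6 / 1.6 | 97% | 97% | 4% |
| 3 vs 3 | 2.4 / 2.4 | 95% | 95% | 1% |

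The first row can be checked by hand: the interval misses whenever no patient is affected, which has probability e^(-1) = 0.37, and 1 - 0.37 = 0.63.

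At 93 PY the pattern is the same, by expected counts: 1/0 63%, 1/0.5 77%, 2/1 86%, 4/1 90%, 10/5 95%. Below one expected patient it is worse (0.5/0 gives 39%). Patient-level simulation with censoring at one year agrees: 1/0 gives 63% without drop-out and 60% with an assumed drop-out hazard of 0.2 per year.

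**Step 3: numerator.** The definition of n, the formula n/T and the first-occurrence exposure rule all use patients; one sentence uses events. For scale, with invented counts: 40 patients with 15 events each and a first event at week 1.5, plus 53 others at 0.9 years, give T = 40 × 1.5/52 + 53 × 0.9 = 48.9 PY. By patients the rate is 40/48.9 = 82 per 100 PY; by events it is 600/48.9, about 1,230.

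**The case against.** The strongest reply is that these are descriptive tables. Protocol Section 10.7 says only that such rates and differences may be provided. SAP Section 9.1 also plans cumulative incidence with pairwise differences and CIs, and serious events, AESIs and deaths are tabulated by patient count and listed. The EAIR tables show patient counts and exposure beside the rate, so a reader can see a 0 vs 0 row for what it is. That limits the consequence and stands. It does not make a zero-width interval a 95% interval.

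Four stronger readings are tempting, and the documents do not support them.

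- That the interval under-covers rare terms in general. At equal rates it covers about 95% to 100%, because the true difference of 0 lies inside [0, 0]. (If the comparator were a single matched placebo group, at an assumed 46.5 PY, equal rates give 91% to 100%.)
- That it creates false signals. At 4 vs 0 and 80 PY the SAP interval is 0.1 to 9.9 and excludes zero, but the score interval, 0.2 to 12.9, excludes it too. Only the more conservative exact-based interval (-0.9 to 12.8) does not. With equal exposure, the score statistic at zero difference is the same as E, (n_z - n_p)/√(n_z + n_p), which is 2.00 here. There is no case for removing E beyond 0/0.
- That these intervals decide the safety conclusion. No decision rule in either document uses them.
- That EAIR will be computed from events. The formula, the definition of n and the exposure rule already point to patients, so this is a wording conflict, and the 1,230 figure arises only if a programmer follows the one sentence against the rest.

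**Conclusion.** The point holds in a limited form. The collapse to [0, 0], and the undefined E, follow from the formula alone. The shortfall in coverage, about 63% to 90% against a nominal 95%, is conditional: it needs true rates that differ, with roughly 1 to 2.5 patients expected on drug and 0 to 1 on placebo, at an assumed 80 PY per arm. Those rates and that exposure are assumptions, not figures from the documents. A real difference in a rare term is nevertheless a case that a safety comparison should be able to describe, and the score interval covers about 98% to 100% in the same scenarios. The numerator conflict is real but editorial. Efficacy is not affected.

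**What to change.** In SAP Section 9.1.12:

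1. Replace the normal-approximation interval with the score (Miettinen-Nurminen type) interval for a difference of two rates.
2. State that E is reported as not calculable when neither compared arm has an affected patient.
3. Reword the EAIR sentence to the number of patients with at least one event per 100 patient-years, so that it matches n/T and the first-occurrence exposure rule.

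The cost is SAP wording and a short macro change. Intervals for rare terms become wider: at 1 vs 0 and 93 PY per arm, -3.1 to 6.1 per 100 PY instead of -1.0 to 3.2. No new data are needed.
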